**Serial no: 0304707**

**9/13/2020**

## **Impact of Zinc to Copper ratio and Lipocalin -2 in Obese Patients Undergoing Sleeve Gastrectomy.**

[name], [name], [name]

Department of Clinical Pathology Alexandria University Hospitals; Department of Surgery  
Alexandria University Faculty of Medicine.

Obesity represents tremendous threat to health globally. WHO conveyed that over 10% of the world's population were classified as obese in 2016, which signifies 3-fold increase in frequency of obesity since 1975. Laparoscopic Sleeve Gastrectomy (LSG) has proved to be an effective procedure for achieving considerable weight loss with significant improvement in obesity-related comorbidities.

A possible role of trace elements in the pathogenesis of obesity has been largely ignored. In particular zinc (Zn) and Copper (Cu) are crucial TE, that act as structural ions in hormones, proteins and receptors and cofactors in various enzymatic reactions. It has been theorized that balance between Zn and Cu has an influence on antioxidant mechanisms and development of associated comorbidities. Nevertheless, few studies have systematically evaluated TE in morbidly obese patients undergoing bariatric surgery.

Lipocalin 2 (Lcn2), also known as NGAL (neutrophil gelatinase-associated lipocalin), Lcn2 is adipokine that belongs to lipocalin family. It is a 25- KD  $\alpha$ -glycoprotein originally identified in human neutrophils. Lcn2 overexpression in adipose tissue stimulates the production of pro-inflammatory cytokine as interleukin 6 (IL-6) and receptor activator of NF- $\kappa$ B ligand.

The aim of the current study primarily was to investigate the value of zinc to copper ratio as possible biomarker of TE imbalance in morbidly obese subjects undergoing LSG. Secondly to correlate it with lipocalin 2 (Lcn2) with respect to Anthropometric measurements and other metabolic markers prospectively.

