#### **Outcome measures:**

primarily was to investigate the value of zinc to copper ratio as possible biomarker of TE imbalance in morbidly obese subjects undergoing LSG.

For detection of presence of micronutrient deficiency in morbid obesity in form of zinc to copper ratio and re-evaluate it after loss of weight

Secondly to correlate it with lipocalin 2 (Lcn2) with respect to Anthropometric measurements and other metabolic markers prospectively.

As zinc to copper ratio is considered as biomarker of micronutrient status; therefore, correlate it with other biomarkers of inflammation (lipocalin 2) and other parameters as BMI, FBG to determine if micronutrient status improve after weight loss or not

**Time frame:** 9 months.

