### **Biochemical parameters**

Fasting blood samples will be collected from participants prior to surgery and nine months postoperative, after overnight fast and divided into two tubes; EDTA for complete blood count, the rest into plastic tubes and serum sample.

Serum glucose and Total cholesterol, HDL- cholesterol, LDL- cholesterol, and triglyceride, total protein and Albumin. Serum iron (Fe), and ferritin.

Serum insulin, Ceruloplasmin, Zn and Cu levels, CRP and lipocalin-2 (Lcn2) .

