### **Statistical analysis**

All data will be analyzed with Statistical Package for the Social Sciences version 20 software (SPSS, Inc., Chicago, IL). Results will be displayed as mean  $\pm$  SD. Paired Student's t-test used to compare the data pre-operative and nine months postoperative. The chi-squared test used for category variables. Spearman correlation coefficient used to detect the correlation between different variables. Statistical correlations calculated by Pearson's correlation test.  $P < 0.05$  is considered significant.

[name]

Consultant Clinical Pathology at Alexandria University Hospitals

Alexandria University, Faculty of Medicine Alexandria University Hospitals

Mobile [contact]

Faculty contact no: [name]

Email: [contact]

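### The planned correlations name only the zinc-to-copper ratio, which cannot show whether zinc, copper or both relate to the marker; no separate zinc or copper analysis is specified

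*Combined protocol and SAP*

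**What the plan says.** The aim, in the opening section, and the Outcome measures section both give the ratio as the trace-element variable to be correlated. The aim reads "Secondly to correlate it with lipocalin 2 (Lcn2) with respect to Anthropometric measurements and other metabolic markers prospectively", where the pronoun stands for the zinc-to-copper ratio. Outcome measures repeats this and adds the instruction to "therefore, correlate it with other biomarkers of inflammation (lipocalin 2) and other parameters as BMI, FBG".

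The ratio is given a specific meaning. The primary aim is to "investigate the value of zinc to copper ratio as possible biomarker of TE imbalance in morbidly obese subjects undergoing LSG", and the correlation sentence opens with "As zinc to copper ratio is considered as biomarker of micronutrient status".

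The Biochemical parameters section, which covers the preoperative and nine-month samples, lists "Serum insulin, Ceruloplasmin, Zn and Cu levels, CRP and lipocalin-2 (Lcn2", so both metals are available singly at both times.

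The Statistical analysis section offers two correlation methods: "Spearman correlation coefficient used to detect the correlation between different variables" and "Statistical correlations calculated by Pearson's correlation test". It lists no variables, includes no regression with more than one explanatory variable, and neither plans nor rules out correlations of zinc or copper on their own.

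**The concern.** On the log scale the ratio is log zinc minus log copper. Using it as the single explanatory variable assumes that the two metals relate to the marker with equal and opposite strength. The plan specifies no analysis that would check this, although it collects the data to do so.

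Two misreadings follow. If lipocalin-2 follows copper and has nothing to do with zinc, the ratio still correlates with lipocalin-2, and under the plan's reading this is reported as trace-element imbalance or micronutrient status. If lipocalin-2 rises with both metals, the two contributions pull against each other in the ratio, and a real association may be missed or may take the sign of the stronger metal.

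The whole secondary outcome is exposed. The primary aim is touched as well, because the value of the ratio as a biomarker cannot be judged without setting it beside its two components.

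**Working it through.** **Design figures.** The documents contain no sample-size calculation, target correlation, or mean or SD for zinc, copper or the ratio, so there is no planned figure to reproduce. The completer count is consistent: 120 - 13 = 107 = 69 + 38.

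**Inputs from the documents.** n = 107 at nine months (participant numbers at the end of the study) and a 0.05 significance level (Statistical analysis), taken as two-sided. The plan does not say whether the correlations use preoperative values, nine-month values or changes. n = 107 suits the last two; preoperative correlations could use up to 120.

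**Assumed inputs.** The log-scale SDs of zinc (s_Zn) and copper (s_Cu), the zinc-copper correlation (rho), and the correlation of each metal with the marker (r_Zn, r_Cu).

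**Formula.** Because log(Zn/Cu) = log Zn - log Cu,

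r(ratio, marker) = (r_Zn·s_Zn - r_Cu·s_Cu) / sqrt(s_Zn² + s_Cu² - 2·rho·s_Zn·s_Cu).

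The chance of P<0.05 uses Fisher's z: m = atanh(|r|)·sqrt(n - 3), power = Φ(m - 1.96) + Φ(-m - 1.96).

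**Two different truths, one statistic** (s_Zn = 0.15, s_Cu = 0.20, rho = 0; denominator sqrt(0.0225 + 0.04) = 0.25):

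- Copper only, r_Cu = 0.35, r_Zn = 0: r = (0 - 0.070)/0.25 = -0.28.
- True balance, r_Zn = -0.2, r_Cu = +0.2: r = (-0.030 - 0.040)/0.25 = -0.28.
- In both cases m = 0.2877 × 10.198 = 2.93, and power is about 83%.

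**Same direction**, r_Zn = r_Cu = 0.30, same SDs: r = (0.045 - 0.060)/0.25 = -0.06, power 9%. The ratio correlation is exactly zero only when r_Zn·s_Zn = r_Cu·s_Cu.

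**Range over the assumptions** (percentage of studies with P<0.05 for the ratio):

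| s_Zn / s_Cu | rho | Copper only, r_Cu = 0.35 | r_Cu = 0.2 | r_Cu = 0.1 | Both +0.3 |
|---|---|---|---|---|---|
| 0.15 / 0.20 | 0 | 83 | 38 | 13 | 9 |
| 0.15 / 0.15 | 0 | 73 | 31 | 11 | 5 |
| 0.20 / 0.15 | 0 | 58 | 23 | 9 | 9 |
| 0.12 / 0.25 | 0 | 91 | 46 | 15 | 30 |
| 0.15 / 0.20 | 0.2 | 91 | 45 | 15 | 10 |
| 0.15 / 0.15 | 0.2 | 83 | 37 | 13 | 5 |
| 0.20 / 0.15 | 0.2 | 68 | 28 | 10 | 10 |
| 0.12 / 0.25 | 0.2 | 95 | 53 | 17 | 35 |

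In the rows with rho = 0.2, copper only means that zinc has no simple correlation with the marker.

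**What component results add.** Simulated Spearman tests on the raw ratio (3,000 runs, both log-SDs 0.15, rho = 0) gave these rejection rates:

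| Truth | Ratio | Zinc | Copper |
|---|---|---|---|
| Copper only, r_Cu = 0.4 | 80% | 5% | 99% |
| Balance, -0.2 / +0.2 | 81% | 50% | 51% |
| Both +0.3 | 5.5% | 84% | 86% |

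The ratio column does not separate the first two rows and misses the third. The component columns help with the first two and detect the third. With log-SDs 0.15/0.20 and both correlations +0.30, a joint regression on log zinc and log copper rejects in 99% of studies, against 9% for the ratio.

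**Is a test of equal and opposite coefficients enough?** No. In the copper-only case (r_Cu = 0.35, SDs 0.15/0.20, rho = 0) it rejects in only about 61-62% of studies. In about 30% of such studies the ratio is significant, the coefficients have opposite signs and the test does not reject, so a rule built on non-rejection would call them ratio findings. With SDs 0.12/0.25 the figure is about 45%.

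**The case against.** The ratio was chosen deliberately and has a stated rationale in the opening section, the aim at issue is secondary and correlational, and every size above depends on assumed inputs. The last part stands: only n and the significance level come from the documents, and the assumed copper-marker correlation drives the result most. At 0.1 a copper-only association makes the ratio significant in no more than 17% of studies. The deliberate choice of a ratio does not answer the point, because the inability to tell one metal from the other is a matter of algebra and holds whatever the spreads are.

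Four stronger readings are tempting and are not supported.

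- A reader might infer that the plan correlates nothing but the ratio. The Statistical analysis section speaks of correlation between variables that it does not list, so zinc and copper alone are not excluded. What can be said is that no separate analysis is specified. Component results chosen after the data are seen would not repair that.
- A reader might infer that same-direction associations always cancel. Full cancellation is a special case. With SDs 0.15/0.20 and independent metals, r_Zn = 0.2 with r_Cu = 0.4 still gives the ratio 54% power. Nor do the documents suggest that lipocalin-2 rises with both metals.
- A reader might infer that a correlation of the ratio with ceruloplasmin is built in by construction. Ceruloplasmin is not a term of the ratio. Only zinc and copper are, and no such correlation is actually planned.
- A reader might infer that a ratio finding in this study is really a copper finding. The documents report no zinc, copper or ratio values, so nothing can be said about which pattern holds.

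**Conclusion.** The point holds in a limited form. The aim and Outcome measures name the ratio as the only trace-element variable to be correlated and read it as imbalance or micronutrient status. The analysis specified cannot support that reading, because copper-only and true-balance patterns can give the same statistic (-0.28 in both worked cases), and same-direction associations are attenuated. That conclusion needs only the definition of the ratio.

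The size in this study is unknown. Over the assumed inputs, a copper-only association makes the ratio significant in about 58-95% of studies at r_Cu = 0.35, 23-53% at 0.2 and 9-17% at 0.1, and r = 0.3 with both metals does so in 5-35%. These are illustrations at n = 107, not estimates. The change is inexpensive and worth making; the ratio analysis itself can stay.

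**What to change.** In Outcome measures and Statistical analysis, add that for every marker correlated with the ratio, the marker will also be regressed on log zinc and log copper together, and that both coefficients with 95% confidence intervals will be reported beside the ratio correlation.

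State how the results will be read:

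- A ratio correlation is described as zinc-copper balance only where the two coefficients and their intervals support contributions from both metals in opposite directions.
- Failure to reject equal and opposite coefficients is not taken as support for balance.
- Otherwise the result is reported as a zinc association, a copper association, or unresolved.
- Correlations of the ratio with zinc or copper are not used as evidence for the marker, because the ratio is built from them. With log-SDs 0.15/0.20 and independent metals they are +0.15/0.25 = +0.6 and -0.20/0.25 = -0.8 by construction.

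The document already tabulates nine-month results, so the addition should be dated and marked as made after data collection if that is the case.

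The cost is one more regression per marker, with no new samples or visits. The price in interpretation is wider intervals for the single-metal coefficients, and some ratio findings may become single-metal or unresolved ones. In the simulated balance case above, each metal alone reached significance in only about half of studies.

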#### **Follow-up and outcome parameters:**

All studied subjects will be followed up for early postoperative complications (within the first month) as Bleeding or Leak. Then they will be reviewed after 9 months postoperatively for assessment of anthropometric measurements, control of preoperative comorbidities, and manifestations of TE deficiencies (anemia, hair loss, teeth problems, edema. etc.).

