#### **Pre-assignment Details**

adult morbidly obese subjects were included age above 20 years, BMI above 40

Suffering from comorbidities as hypertension, DM, dyslipidemia.

Assigned participants were clinically evaluated for comorbidities as hypertension, DM, dyslipidemia.

As well as signs of nutritional deficiency as anemia, brittle nails.

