### **Group Information**

one group of participants eligible for laparoscopic sleeve gastrectomy were assigned according to their will to participate in study.

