#### **Period of evaluation:**

First visit: preoperative for clinical assessment of participants, determine BMI and waist circumference and withdrawal of serum blood sample

Second visit: within one month after surgery to make sure that no complication occurred after surgery.

Third visit: nine months postoperative for revaluation of participants, determine BMI and waist circumference, and withdrawal of a serum blood sample

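### Drug treatment for hypertension, diabetes and dyslipidemia is not a listed assessment, so 9-month changes in blood pressure, lipids, glucose and HOMA-IR cannot be separated from treatment changes

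*Combined protocol and SAP*

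**What the plan says.** Pre-assignment Details gives age and BMI limits and then "Suffering from comorbidities as hypertension, DM, dyslipidemia". It adds: "Assigned participants were clinically evaluated for comorbidities as hypertension, DM, dyslipidemia". Group Information describes a single group: "one group of participants eligible for laparoscopic sleeve gastrectomy were assigned according to their will to participate in study".

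Period of evaluation sets the content of the two measurement visits: "First visit: preoperative for clinical assessment of participants, determine BMI and waist circumference and withdrawal of serum blood sample" and "Third visit: nine months postoperative for revaluation of participants, determine BMI and waist circumference, and withdrawal of a serum blood sample". Under Follow-up and outcome parameters, patients are to be "reviewed after 9 months postoperatively for assessment of anthropometric measurements, control of preoperative comorbidities", with no definition of control. Biochemical parameters lists fasting glucose, lipids and insulin before surgery and at 9 months.

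Outcome measures makes the zinc to copper ratio the primary interest. The secondary aim is to "correlate it with other biomarkers of inflammation (lipocalin 2) and other parameters as BMI, FBG". The results table gives systolic pressure, lipids and HOMA-IR at both times. Statistical analysis names the paired t-test, the chi-squared test, and Spearman and Pearson correlations, with no covariate or stratum.

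**The concern.** Blood pressure, lipids, glucose and HOMA-IR all respond to drugs given for the three listed conditions. If treatment is started, increased, reduced or stopped in the nine months between the samples, the change in the marker contains a treatment part as well as whatever follows surgery and weight loss. Added treatment would exaggerate an apparent improvement, and withdrawn treatment would hide one. With one group and no treatment variable, the planned analysis cannot tell these apart.

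HOMA-IR is the sharpest case because it is built from fasting glucose and insulin. In a patient injecting insulin, the serum value may partly reflect the injected drug, and stopping it could then look like a fall in insulin resistance.

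At stake are the reading of comorbidity control at 9 months, the metabolic rows of the results table, and the secondary correlations of the zinc to copper ratio with fasting glucose and other metabolic markers.

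**Working it through.** **Step 1: is treatment listed anywhere?**

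| Section | Listed content | Drug treatment named? |
|---|---|---|
| Pre-assignment Details | Clinical evaluation for comorbidities; signs of nutritional deficiency | No |
| Period of evaluation | Clinical assessment or re-evaluation, BMI, waist, blood sample; complication check at one month | No |
| Follow-up and outcome parameters | Early complications, anthropometry, comorbidity control, signs of trace element deficiency | No |
| Anthropometric parameters | BMI, waist | No |
| Biochemical parameters | Laboratory tests | No |
| Statistical analysis | Unadjusted tests and correlations | No |

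**Step 2: which results are exposed?** From the results table:
- Systolic pressure: 146.0 − 132.0 = 14.0 mmHg fall.
- Total cholesterol: 5.85 − 4.64 = 1.21 mmol/L fall.
- LDL cholesterol: 3.37 − 2.97 = 0.40 mmol/L fall.
- HOMA-IR: 2.64 − 1.44 = 1.20 fall, and 1.20 / 2.64 = 45%.

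Fasting glucose is measured and named as a correlate but is not in the table.

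**Step 3: how large could the treatment part be?** The documents give neither the share of patients treated nor any drug effect, so there is no figure to reproduce. For systolic pressure, an illustration on assumed inputs uses

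shift in mean = net share of patients whose treatment changed in one direction × mean effect per changed patient.

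| Assumed net share | 5 mmHg each | 10 mmHg each |
|---|---|---|
| 10% | 0.5 | 1.0 |
| 25% | 1.25 | 2.5 |
| 50% | 2.5 | 5.0 |
| 75% | 3.75 | 7.5 |

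Against the 14 mmHg fall, the extremes are 0.5 / 14 = 4% and 7.5 / 14 = 54%. If treatment was added, the fall net of drugs would be between 14 − 7.5 = 6.5 and 14 − 0.5 = 13.5 mmHg. If it was withdrawn, it would be between 14 + 0.5 = 14.5 and 14 + 7.5 = 21.5 mmHg. Changes in opposite directions partly cancel, so these are one-way extremes.

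**Step 4: HOMA-IR.** Let a share f of patients be on insulin at either visit, with mean fall d_u, and let the rest have mean fall d_o. Then 1.20 = f × d_u + (1 − f) × d_o, so d_o = (1.20 − f × d_u) / (1 − f). Neither f nor d_u is given, so d_o is undetermined.

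**Step 5: the correlations.** No size can be computed for the correlation of the ratio with fasting glucose or any other marker, because the documents give no correlation and no treatment data.

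**The case against.** Several objections have force.

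- **Not listed is not the same as not recorded.** A reader might infer that drug use was never noted. The clinical assessment, the re-evaluation and the review of comorbidity control could each include it. The lists are also incomplete: systolic pressure and leptin appear in the results table but in none of the assessment lists. What stands is that drug use is not specified and that no planned analysis uses it.
- **No treatment change is documented.** A reader might infer that the tabulated falls are partly drug effects. The documents report no drug change and no insulin user, so the supportable statement is only that the two cannot be separated.
- **There is no scoring rule.** It is tempting to say that the plan counts a patient on more drugs as improved, or one taken off drugs as unimproved. The text defines no such categories. Control is simply undefined.
- **Patients are not recruited because of the comorbidities.** Recruitment and Group Information take morbidly obese candidates for sleeve gastrectomy. Whether each must have a listed comorbidity is unclear.
- **The aims do not include estimating surgery's effect on blood pressure or lipids.** This is fair, and it limits the point to secondary and descriptive results. A treated glucose or LDL value is also still the patient's true value at sampling. It remains open to confounding or attenuation in a correlation, but it is not meaningless.
- **The illustration concerns systolic pressure, not the named correlations.** This is correct. It shows scale and does not estimate harm to the secondary aim.

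**Conclusion.** The point holds as an unspecified and unadjusted influence on secondary results. As written, the 9-month changes in blood pressure, lipids, fasting glucose and HOMA-IR, and their correlations with the zinc to copper ratio, cannot be separated from any change in drug treatment.

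The direction and size of any bias are unknown. The range of 0.5 to 7.5 mmHg for systolic pressure rests wholly on assumed shares and effects, with all net change in one direction. Even its upper end leaves 6.5 mmHg of the 14 mmHg fall.

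A reader might go further and conclude that the primary result is compromised, or that the problem is beyond repair. The documents support neither: the change in the ratio is not directly affected, and drug data may still be in the surgical charts. The change is worth making because it is cheap and because HOMA-IR in any insulin-treated patient could otherwise be misread.

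**What to change.** 1. Record antihypertensive, lipid-lowering and glucose-lowering drugs, including insulin, at the preoperative and 9-month visits, in enough detail to classify treatment as reduced, unchanged or increased. For patients already seen, take this from the charts.
2. Define control of each comorbidity and report it together with that treatment status.
3. Leave patients on insulin at either visit out of the HOMA-IR and insulin analyses, and state how many are left out.
4. Show the blood pressure, lipid and fasting glucose changes, and the correlations with the zinc to copper ratio, by treatment status. Label this a descriptive sensitivity analysis only. Treatment change happens after surgery and may depend on response, so the unchanged-treatment subgroup is not an unbiased estimate of the effect of surgery.
5. If drug data cannot be obtained, describe the changes as observed under usual treatment and do not attribute them to surgery or weight loss.

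The cost is a few fields on the visit form or a chart look-up, a smaller number of patients for HOMA-IR, and possible selection in the treatment-status subgroups. The proposal concerns recording and analysis only and asks for no change to any patient's treatment.

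### Only anemia is named as a deficiency sign at both visits and no common checklist is given, so a change in any other sign could not be reliably interpreted

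*Combined protocol and SAP*

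**What the plan says.** Clinical signs of deficiency appear in two places in the combined protocol and SAP.

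- *Pre-assignment Details*, describing the preoperative clinical evaluation, adds to the comorbidities: "As well as signs of nutritional deficiency as anemia, brittle nails".
- *Follow-up and outcome parameters*, describing the 9-month review, lists "manifestations of TE deficiencies (anemia, hair loss, teeth problems, edema. etc", alongside anthropometry and control of comorbidities.

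*Period of evaluation* does not say which signs are examined at either visit. It speaks only of a clinical assessment before surgery and a re-evaluation at nine months.

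The laboratory side is the same at both times. Under *Biochemical parameters*, "Fasting blood samples will be collected from participants prior to surgery and nine months postoperative", with one tube being "EDTA for complete blood count".

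*Outcome measures* expresses deficiency through the serum ratio: "For detection of presence of micronutrient deficiency in morbid obesity in form of zinc to copper ratio and re-evaluate it after loss of weight". It then correlates that ratio with lipocalin 2 and other parameters "to determine if micronutrient status improve after weight loss or not". *Statistical analysis* has one general sentence for categorical data: "The chi-squared test used for category variables".

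**The concern.** This is a single-group study in which each participant is compared with his or her own earlier state. A statement that a sign appeared, persisted or resolved is sound only if the sign was looked for in the same way on both occasions. If hair loss, teeth problems or edema were recorded only at 9 months, long-standing cases could be taken for new ones. If brittle nails were recorded only before surgery, they could seem to have gone because nobody looked again. There is no control group to reveal such an effect, and a baseline examination that was not recorded cannot be reliably reconstructed later.

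What is at stake is limited: any descriptive account of how clinical deficiency signs changed after surgery. These signs are the only non-laboratory evidence of deficiency that the plan collects, and the 9-month list stands under a heading that includes outcome parameters. It is therefore reasonable to expect that something will be reported on them.

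**Working it through.** The documents give no prevalence for any sign and no power or effect figure for signs, so there is no stated number to reproduce. The check is a comparison of the texts.

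**Step 1: the named signs side by side.**

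| Sign | Preoperative (Pre-assignment Details) | 9 months (Follow-up and outcome parameters) |
|---|---|---|
| Anemia | named | named |
| Brittle nails | named | not named |
| Hair loss | not named | named |
| Teeth problems | not named | named |
| Edema | not named | named |

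Two signs are named before surgery and four at 9 months, with one in common: 2 + 4 − 1 = 5 distinct signs. One of the five is named at both visits; four of the five are named at one visit only.

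**Step 2: are the lists closed?** No. The preoperative list is introduced by *as*, which this document uses to mean *such as* (the comorbidities and the early complications are introduced in the same way). The 9-month list ends in *etc.* An examiner may record a sign that is not named. So the table shows what is guaranteed by the text, not what was done.

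**Step 3: does another section supply a common list?** No. *Period of evaluation*, *Anthropometric parameters*, *Biochemical parameters* and *Outcome measures* contain no checklist, definition or grading of clinical signs.

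**Step 4: which signs have an objective measure at both times?** Anemia does, because a complete blood count is planned before surgery and at nine months. For the other four signs the plan names no measurement at both visits.

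**Step 5: does a planned analysis depend on the signs?** None is specified. The primary measure is the zinc to copper ratio, from serum sampled at both times. The chi-squared sentence is tied to no sign, and the preoperative and postoperative results table contains none.

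**Step 6: who is affected?** The document reports 120 participants at the start and 13 lost by 9 months: 120 − 13 = 107 with a 9-month review. All those enrolled are thus accounted for. For the 107, the baseline examination is past, and what remains open is how the signs are reported.

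**The case against.** The strongest case on the other side is that this is loose wording in a very short protocol. Both lists are illustrative, so a competent examiner may well have recorded the same signs each time. The question of micronutrient status is answered through the serum ratio, not through signs. No before-after comparison of signs is planned, and none is in the results table. All of this is correct, and it settles the severity. It does not remove the gap: two differing sets of open-ended examples leave the content of each examination to the examiner, and nothing in the plan prevents a statement about change in, say, hair loss.

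A reader might infer more than the text supports:

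- *That every before-after reading of clinical deficiency is an artefact.* Anemia is named at both visits and backed by a blood count at both, so a comparison of anemia stands.
- *That the bias has a known direction for each sign.* That would need closed lists, and neither list is closed.
- *That the participants would show a calculable false rise in the proportion with any sign.* The plan defines no such composite. A figure for it would rest on assumed prevalences, independence of signs and closed lists, none of which the documents give.
- *That the two visits measure different constructs, because the first speaks of nutritional and the second of trace-element deficiency.* Anemia stands under both labels, and the difference is too slight to carry that conclusion.

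**Conclusion.** The point holds as a minor gap in the standardisation of measurement. One of the five named signs is guaranteed at both visits by the text. A reported change in any of the other four could not be told apart from a change in what was examined. No size can be given for the effect on results, since the documents contain no sign data and plan no test on them.

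The conclusion rests on the text alone, and on the assumption that no separate case record form with a common list exists; if one does, citing it would close the point. The zinc to copper ratio and the other laboratory comparisons are not touched. This is a cheap improvement, not a threat to the primary aim.

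**What to change.** Use one fixed checklist at the preoperative and the 9-month visit, with each item marked present or absent: anemia (from the blood count, by one stated definition), brittle nails, hair loss, teeth problems, edema. Add a one-line definition for each item.

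For subjects already assessed without such a list, limit before-after statements to anemia. Report each other sign only as prevalence at the visit where it was recorded, not as new, changed or resolved. As the document already reports the 9-month follow-up, this is the part that applies to the 107.

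If a change in anemia, or in any sign recorded on a common list, is to be tested, name a paired method such as McNemar's test. The chi-squared test as named does not by itself account for two observations on the same person.

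The cost is one shared page and a few minutes per visit, with no new laboratory test. The downside is that fewer before-after claims can be made from the existing data.
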